7.3 LOST TO FOLLOW-UP

A participant will be considered lost to follow-up if he or she fails to return for 3 consecutive scheduled visits and is unable to be contacted by the study staff.

The following actions must be taken if a participant fails to return to the lab for a required study visit:

- The site will attempt to contact the participant and reschedule the missed visit within 1 week of the missed visit and counsel the participant on the importance of maintaining the assigned visit schedule and ascertain if the participant wishes to and/or should continue in the study.
- Before a participant is deemed lost to follow-up, the investigator or designee will make every effort to regain contact with the participant (where possible, 3 telephone calls will be made to the participant). These contact attempts will be maintained in the study database.
- Should the participant continue to be unreachable, he or she will be considered to have withdrawn from the study with a primary reason of lost to follow-up.

8 STUDY ASSESSMENTS AND PROCEDURES

8.1 EFFICACY ASSESSMENTS

All patients will be cleared by their treating orthopaedic surgeon to complete the tasks in this study prior to enrollment. The orthopaedic surgeon will provide the study team with signed confirmation that the patient has been released to complete the study activities based on their current post-operative recovery (physician release letter) as well as providing the patient's confirmation that they approve the release of their information (patient release of information) so that they are able to be contacted by the study team to determine the patient's interest in participating in the study.

Based on our prior and ongoing studies, we are confident that 40 participants can be enrolled within the 24 month recruitment period. Patients will be identified by his/her treating orthopaedic surgeon as being appropriate for study enrollment at approximately 4.5 months post-ACL reconstruction and safe to complete the study tasks. Once the surgeon and patient have agreed to an interest in study participation and the patient has provided signed consent for release of information, the medical records will be reviewed by a member of the study team to determine enrollment eligibility based on study inclusion and exclusion criteria. All potentially eligible patients (parents if the patient is a minor) will be approached by the treating orthopaedic surgeon or member of the surgeon's clinical staff. If the patient is over the age of 18, he/she will be approached directly by the treating orthopaedic surgeon. During this discussion, the treating surgeon will explain the activities to be completed during the study and will provide the patient with documentation that the surgeon believes the patient is medically appropriate for study enrollment. The referring physicians have been working with the research study team on the recruitment and enrollment of ACL reconstruction patients for the last year on an industry

sponsored knee brace study. During this time the study team has been able to implement a successful recruitment procedure in which the patients are identified by the physician extenders or the surgeon and the above described procedure has been completed in each clinic. If a patient is interested in participating, the signed consent to release information is sent to the research study team and the secondary medical record screening is completed. Informed consent and assent will be approved by the institutional review board.

Prior to the start of the study, all participants (and parents will complete parental permission and patient will complete ascent if participant is <18 years old) will complete informed consent in person in the lab. The consent form will be sent to the potential participant by email or mail based on the patient's preference prior to study enrollment. Potential participants (parents if the potential participant is a minor) will be allowed to review the consent form prior to his/her first visit to the lab. Each participant will be allowed ample time to review the consent form and determine if he/she is interested in participating in the study. All questions will be answered prior to the consent form being signed and the study being initiated. If a consented subject becomes 18 during the course of the study he/she will be consented as an adult at the next study visit.

Following administration of the consent and HIPAA authorization, we will measure height and weight and determine BMI. If female participants become pregnant, their active involvement in the study will end because later stage pregnancy will alter movement mechanics due to increased joint laxity. In addition, weight gain would also likely confound study results. As part of the telephone screening process, women will be excluded if they self-report being pregnant or planning to become pregnant.

We will aim to ensure that subject selection is equitable and all relevant demographic groups have access to study participation by contacting all patients who meet inclusion / exclusion criteria, regardless of demographic characteristics. We have also aimed to produce recruitment and intervention materials that are appropriate for individuals with low literacy or education levels. We will continue to recruit patients until we reach our sample size goal of n=40.

Screening questionnaire data will be entered directly into the study database. We will have paper copies of screening questionnaires that may be used in cases of computer network failure. We anticipate this will be rare. However, if paper forms are needed, data will then be entered as soon as possible. Any paper copies that are used will be stored in the subject's individual study folders which are kept in a locked file cabinet in a locked office of a study team member.

Subject data for all subjects enrolled in the study will be entered into a secure computerized enrollment log. This data will be accessible only to study personnel needing access to fulfill their study related duties.

8.2 SAFETY AND OTHER ASSESSMENTS

Following recruitment and the completion of informed consent, each subject will be asked to complete an initial biomechanical assessment in the Kevin P. Granata Biomechanics Lab at Virginia Tech. All subjects will be asked to wear form fitting shorts and a shirt, plus a pair of athletic shoes (Nike Pegasus, Nike Inc, Beaverton, CO) all of which will be provided for them to use during testing (Figure 2). Previous literature has shown that differences in footwear can alter the ground reaction forces.^{35,38} Therefore in a between-subject design comparing two

groups (Aim 1) it is important to alleviate any potential differences due to footwear. Patients will warm up by cycling on a stationary bike at a comfortable pace for 5 minutes. The seat height for the bike will be standardized for all subjects so that when the leg is fully extended at the bottom of the pedal stroke there will be between 5 and 10 degrees of knee flexion. The seat settings will then be recorded on the data collection sheet and entered into REDCap in order to ensure that the same seat settings are used at each visit. After the warm-up, patients will have retro-reflective markers attached at specific locations on both lower extremities to track segmental motion during both squatting and landing. Three-dimensional coordinate data will be collected using a 10-camera motion capture system at a sampling rate of 120 Hz (Qualysis, Sweden). Ground reaction forces will be collected using 2 embedded force plates at a sampling rate of 2400 Hz (AMTI, Watertown, Massachusetts). Each subject will be asked to complete a standing trial followed by a series of squatting and landing trials as described below:

Squatting trial: Subjects will be asked to complete 15 bilateral squats. Subjects will be asked to stand with their feet shoulder width apart (one foot on each force plate) with their hands in front on them with the shoulder flexed to 90 degrees for counter weight. The foot width will be standardized to ensure that foot placement is consistent for both the squatting trials as well as during the biofeedback training. The subject will be asked to squat down until their thighs are parallel with the ground or until their heels begin to come off of the ground. A stool will be placed behind the subject and will be set to the height where the subject's thigh will be parallel to the ground if they sat down (the stool will be placed at the height of the popliteal fold), so that the subject will know the deepest position they have to achieve. The stool will be placed within 0.5 inches of the desired location using a height adjustable plyobox and dense foam padding. The height setting of the plyobox will be recorded for each subject on the data collection form and will subsequently be entered into REDCap to ensure that the same plyobox position is used during each assessment and each biofeedback session. If the subject is able to achieve a squat position where the thigh is parallel to the floor they will be instructed to squat until they barely touch down on the bench and then slowly stand back up without transferring any weight to the bench. The squat assessment will be completed so that the exact same setup and protocol will be used for the biofeedback training program and obtain a baseline measure of skill during a squat. Upon completion of the squatting trials, subjects will be asked to complete 10 vertical stop-jump tasks. The stop-jump task was selected based on its game-like nature. The stop-jump task is a good simulation of a basketball jump-shot or heading a soccer ball and therefore could produce loads and movements that are closely related to those seen during game play.

Landing trial: Subjects will be asked to complete 10 trials of a vertical stop-jump task. During the vertical stop-jump task, subjects will run straight forward for up to 5 steps taking off on 1 foot, landing on 2 feet (one foot on each force plate), and taking off again on 2 feet.^{16,18,20,21} Prior to testing maximum jump height will be determine using a vertec. During testing, a ball will be hung above the force plates at 75% of the subject's maxmum jump height to provide a target during jumping. Subjects will be instructed to jump up and grab the ball and then come down bilaterally on the two force plates. No instructions will be provided on how to land or what to do with their arms to initiate the jump. The stop-jump task will be used to determine if the biofeedback intervention is effective at decreasing secondary ACL risk factors as these risk factors were determined during landing. Subjects will be allowed to practice the task between 3 and 5 times until they are comfortable with the movement. A minimum of 5 minutes' rest will be given between conditions to minimize the effects of fatigue. If the results of the baseline jumping assessment indicates that the subject has a limb symmetry index (LSI) of greater than or equal to 90%, which is indicative of limb symmetry during hopping in healthy subjects, he/she will be excluded from the intervention.

8.3 ADVERSE EVENTS AND SERIOUS ADVERSE EVENTS

8.3.1 DEFINITION OF ADVERSE EVENTS (AE)

Adverse Event (AE) – Any untoward or unfavorable medical occurrence in a clinical research study participant, including any abnormal sign (e.g. abnormal physical exam or laboratory finding), symptom, or disease, temporally associated with the participants' involvement in the research, whether or not considered related to participation in the research.

8.3.2 DEFINITION OF SERIOUS ADVERSE EVENTS (SAE)

An adverse event (AE) or suspected adverse reaction is considered "serious" if, in the view of either the investigator or sponsor, it results in any of the following outcomes:

- Results in death
- Is life threatening, or places the participant at immediate risk of death from the event as it occurred
- Requires or prolongs hospitalization
- Causes persistent or significant disability or incapacity
- Results in congenital anomalies or birth defects
- Is another condition which investigators judge to represent significant hazards

Important medical events that may not result in death, be life-threatening, or require hospitalization may be considered serious when, based upon appropriate medical judgment, they may jeopardize the participant and may require medical or surgical intervention to prevent one of the outcomes listed in this definition.

8.3.3 CLASSIFICATION OF AN ADVERSE EVENT

8.3.3.1 SEVERITY OF EVENT

For adverse events (AEs) not included in the protocol defined grading system, the following guidelines will be used to describe severity.

- **Mild** – Events require minimal or no treatment and do not interfere with the participant's daily activities.
- **Moderate** – Events result in a low level of inconvenience or concern with the therapeutic measures. Moderate events may cause some interference with functioning.
- **Severe** – Events interrupt a participant's usual daily activity and may require systemic drug therapy or other treatment. Severe events are usually potentially life-threatening or incapacitating. Of note, the term "severe" does not necessarily equate to "serious".

8.3.3.2 RELATIONSHIP TO STUDY INTERVENTION

All adverse events (AEs) must have their relationship to study intervention assessed by the clinician who examines and evaluates the participant based on temporal relationship and his/her

clinical judgment. The degree of certainty about causality will be graded using the categories below. In a clinical trial, the study product must always be suspect.

- **Related** – The AE is known to occur with the study intervention, there is a reasonable possibility that the study intervention caused the AE, or there is a temporal relationship between the study intervention and event. Reasonable possibility means that there is evidence to suggest a causal relationship between the study intervention and the AE.
- **Probably Related** – There is evidence to suggest a causal relationship, and the influence of other factors is unlikely. The clinical event occurs within a reasonable time after administration of the study intervention, is unlikely to be attributed to concurrent diagnosis.
- **Not Related** – There is not a reasonable possibility that the administration of the study intervention caused the event, there is no temporal relationship between the study intervention and event onset, or an alternate etiology has been established.

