2.3 RISK/BENEFIT ASSESSMENT

2.3.1 KNOWN POTENTIAL RISKS

There is a potential risk that participants could injure his/her foot, ankle, or knee or feel off balance while completing these tasks; however, the study team will ensure that the testing area is clean and free of debris. The risk again will be no greater than if the participant were performing these tasks on his/her own and are no more difficult than the sporting tasks that the participant's physician has allowed you to start doing during sport participation or what the participant would be doing at this point during physical therapy. There is a potential risk to the participant's confidentiality. Every effort will be made to maintain his/her confidentiality, however this cannot be guaranteed.

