8.3.4 TIME PERIOD AND FREQUENCY FOR EVENT ASSESSMENT AND FOLLOW-UP

The occurrence of an adverse event (AE) or serious adverse event (SAE) may come to the attention of study personnel during study visits and interviews of a study participant presenting for medical care, or upon review by a study monitor.

All AEs including local and systemic reactions not meeting the criteria for SAEs will be captured on the case report form (CRF). Information to be collected includes event description, time of onset, clinician's assessment of severity, relationship to study product (assessed by the study clinician), and time of resolution/stabilization of the event. All AEs occurring while on study must be documented appropriately regardless of relationship. All AEs will be followed to adequate resolution.

Any medical condition that is present at the time that the participant is screened will be considered as baseline and not reported as an AE. However, if the study participant's condition deteriorates at any time during the study, it will be recorded as an AE.

Changes in the severity of an AE will be documented to allow an assessment of the duration of the event at each level of severity to be performed. AEs characterized as intermittent require documentation of onset and duration of each episode.

The study principle investigator and either of the research assistants will record all reportable events with start dates occurring any time after informed consent is obtained until 7 (for non-serious AEs) or 30 days (for SAEs) after the last day of study participation. At each study visit, the investigator will inquire about the occurrence of AE/SAEs since the last visit. Events will be followed for outcome information until resolution or stabilization.

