8.4 UNANTICIPATED PROBLEMS

8.4.1 DEFINITION OF UNANTICIPATED PROBLEMS (UP)

The Office for Human Research Protections (OHRP) considers unanticipated problems involving risks to participants or others to include, in general, any incident, experience, or outcome that meets **all** of the following criteria:

- Unexpected in terms of nature, severity, or frequency given (a) the research procedures that are described in the protocol-related documents, such as the Institutional Review Board (IRB)-approved research protocol and informed consent document; and (b) the characteristics of the participant population being studied;
- Related or possibly related to participation in the research (“possibly related” means there is a reasonable possibility that the incident, experience, or outcome may have been caused by the procedures involved in the research); and
- Suggests that the research places participants or others at a greater risk of harm (including physical, psychological, economic, or social harm) than was previously known or recognized.

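### The adverse-event causality grade asks only about the study intervention, so an injury on the study's own landing test has no code of its own and can be misattributed

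*Combined protocol and SAP*

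**What the plan says.** Section 8.3.3.2 sets the only causality scale for adverse events: "All adverse events (AEs) must have their relationship to study intervention assessed by the clinician who examines and evaluates the participant". There are three categories. *Related* can be met in several ways, one of which is simply that "there is a temporal relationship between the study intervention and event". *Not Related* applies where "There is not a reasonable possibility that the administration of the study intervention caused the event", or where "there is no temporal relationship between the study intervention and event onset, or an alternate etiology has been established". *Probably Related* also refers to the intervention.

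The other parts of event classification use the same reference point:

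- Section 8.3.4 lists what goes on the case report form, including "relationship to study product (assessed by the study clinician".
- Section 8.3.3.3 judges expectedness against the risks described for the intervention.
- Section 8.3.5 gives the investigator and medical monitor the task of relating the event to the intervention.

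The landing test stands apart, under the assessments in Section 8.2: "Subjects will be asked to complete 10 trials of a vertical stop-jump task". Section 2.3.1 accepts that participants "could injure his/her foot, ankle, or knee or feel off balance while completing these tasks". For unanticipated problems, Section 8.4.1 uses a wider standard that includes whether the "outcome may have been caused by the procedures involved in the research".

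**The concern.** The most demanding activity the trial imposes is a test, not a treatment. Biofeedback sessions consist of two squat exercises (6.1.1), and controls receive education with no added exercise (4.2). A scale that asks only whether the intervention caused the event cannot say that the test did. The grading clinician must either call a test injury unrelated or, if a training session was recent, call it related to training. Neither is an accurate record.

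At stake is what the pilot can tell the planned multi-center trial about harm: whether any injuries came from the training or from the assessment. If the next trial keeps the same stop-jump assessment, that distinction bears on its risk statement and its consent form.

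**Working it through.** The plan states no figure on this point. The check is to count the exposure and then apply the three categories to one and the same injury.

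**Exposure to jump-landing, per participant completing all assessments**

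- Recorded trials per assessment: 10 (8.2). Assessments: 3, at baseline, 6 and 12 weeks, in both arms (5.5).
- Recorded stop-jumps: 10 × 3 = 30. Each has two bilateral landings (land, jump again, come down on both plates), so 30 × 2 = 60.
- Practice: 3 to 5 jumps (8.2). The text does not say whether practice is repeated at each visit. If done once, the total is 30 + 3 = 33 to 30 + 5 = 35. If repeated, it is 3 × (10 + 3) = 39 to 3 × (10 + 5) = 45.
- The maximum-jump measurement comes on top, with no stated number of attempts.
- Stop-jumps within either intervention: 0.

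**The same stop-jump injury under 8.3.3.2**

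| When | Biofeedback arm | Control arm |
|---|---|---|
| Baseline, before randomization (6.3) | *Not Related* only | *Not Related* only |
| Week 6 | *Related* by timing if a session was recent, or *Not Related* because the test is an established other cause | *Not Related* is the natural code. *Related* by timing is possible if education counts as intervention |
| Week 12 | As at week 6, but the last session is about 6 weeks earlier, so the timing route is weaker | As at week 6, with the same weakening |

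Three further points bear on the table.

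1. At week 6 two opposite categories can both be satisfied, and 8.3.3.2 gives no order of precedence. It also says that the study product is always to be suspected, which leans toward *Related*.
2. The trial is open (6.3). Section 4.1 blinds the technician who runs the tests, but nothing says that the clinician who grades events is masked.
3. Whether education counts as intervention is unclear. Section 6.1.1 and the schedule in 1.3 treat the control sessions as interventions, and one falls in week 6. Section 5.5 describes controls as those not in the patient intervention arm.

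**Baseline events and the safety set.** People who show a limb symmetry index of 90% or more on the baseline jumps are excluded after doing them (5.2, 8.2). The safety set in 9.3 requires an intervention visit. A baseline test injury in someone who never starts sessions is therefore outside the safety analysis, although it is recorded, because recording starts at consent (8.3.4).

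**The case against.** The strongest reply is that little depends on this grade. Section 8.3.4 has every event documented whatever its relationship, with a description and time of onset. Section 8.3.5 sends all events to the safety officer twice a year, and 9.4.4 lists or summarizes them monthly. Section 8.3.6 has serious events reported whether or not they are thought related. Section 8.4.1 makes its own judgement against the research procedures, and nothing says that it takes its answer from 8.3.3.2. Internal notification in 8.3.5 covers events related to the study. All of this stands. A reader might infer that a hazardous test could continue unnoticed, but the documents do not support that.

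A reader might also infer that every test injury is coded *Not Related*, or that biofeedback test injuries would be coded *Related* while control injuries never would. Neither follows. The first is certain only at baseline. The second ignores the alternate-cause route in the biofeedback arm and the possible timing route in the control arm. Nor is a between-arm comparison of related events planned that could be biased: 9.4.4 promises only lists and summaries.

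Finally, the adverse-event form is an appendix to the manual of procedures, which is not among the documents supplied. It may already have a field for procedures or activity.

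What survives is narrower. The wider standards in 8.3.5 and 8.4.1 require a judgement about study procedures, but the grading rule and the listed form content provide no place to record one. That judgement can then sit beside a recorded grade that says something different.

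**Conclusion.** The point holds as a gap in attribution. The causality grade and the listed form item refer only to the intervention, while all jump-landing, at least 30 recorded stop-jumps per completing participant, lies in testing done by both arms. A baseline test injury can only be graded *Not Related*. A later one can be graded either way, so identical injuries may be graded differently between participants and arms. The result is a safety record in which harm from testing may be credited to training or to nothing. Events are not lost and reporting is not delayed.

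No expected number of misgraded events can be given. The documents state no injury risk for the test, and any figure would also need an assumption about how clinicians choose between the overlapping categories. The conclusion assumes that the unseen form follows 8.3.4. If it already records relationship to procedures, only the text needs aligning. This is a worthwhile, inexpensive improvement for a pilot meant to inform a larger trial.

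**What to change.** In 8.3.3.2, 8.3.4 and the adverse-event form, record two ratings for every event in both arms: (a) relationship to the assigned intervention and (b) relationship to study procedures, meaning the biomechanical testing. Record the activity during which the event occurred. In addition:

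- State that timing alone does not make an event intervention-related when it occurred during testing, and make the categories mutually exclusive.
- State whether the education sessions count as study intervention for rating (a).
- Treat a positive answer on either rating as related to the study for 8.3.5, 8.3.6 and 8.4.1.
- Summarize (a) and (b) by arm, including baseline-test events. Report separately those in people who were never randomized, who have no arm and fall outside the 9.3 safety set.

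The cost is one extra rating field and a few sentences of text. The activity can go in the event description already collected. No visits, staff or participants are added. The count of research-related events may rise, because test injuries now graded unrelated would be counted.

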8.3.5 ADVERSE EVENT REPORTING

All AEs are collected, analyzed, and monitored by using an Adverse Event Form (MOOP Appendix G). AEs and/or laboratory abnormalities identified in the protocol as critical to participant safety will be reported to the NIAMS and the safety officer. All AEs experienced by a participant during the time frame specified in the protocol (from the initial day of testing as well as the initiation of the biofeedback program through the end of the study) will be reported, as outlined in the protocol (Section 1a of the MOOP).

The procedure for collecting and reporting AEs will be detailed in the following sections. This information will include the role of the Principal Investigator and the Medical Monitor ([name]) in assigning severity and defining the relationship between the AE and the study intervention. A sample AE form can be found in Appendix G. Requirements for reporting AEs to the NIAMS and the study's independent Safety Officer (SO)) is described below.

The Principal Investigator (PI) and study staff members will be responsible for the safety of study participants. It is not anticipated that there will be any significant physical or psychological risks associated with this study. However, federal regulations require prompt reporting to the Virginia Tech Institutional Review Board (IRB), all injuries, adverse events, or other unanticipated problems involving risks to subjects or others that occur in the course of a subject's participation in this research study.

Study team members who become aware of any adverse event related to the study will notify the principal investigator, [name], immediately. Study team members will have contact information for [name] for daytime, evening and weekend hours. If [name] is not available for contact when a study team member becomes aware of a study-related adverse event, [name] or [name], co-investigators on the study, will be contacted. Once [name] (or a co-investigator) is contacted about the adverse event, she / he will make a determination about the reporting requirements in accordance with the Virginia Tech IRB guidelines. This will include notification of the Virginia Tech IRB within 24-hours if a study-related death, within 5 business days if another serious adverse event, and within 10 business days if a protocol deviation/violation, or other unanticipated problem.

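### The causality scale in section 8.3.3.2 makes Related an easier test than Probably Related and lets one event be both Related and Not Related, so the label is not reproducible

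*Combined protocol and SAP*

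**What the plan says.** Section 8.3.3.2 of the combined protocol and SAP presents its three categories as a graded scale: "The degree of certainty about causality will be graded using the categories below".

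- **Related** is met if the event is known to occur with the intervention, if causation by it is a reasonable possibility, "or there is a temporal relationship between the study intervention and event". The section then defines its middle term: "Reasonable possibility means that there is evidence to suggest a causal relationship between the study intervention and the AE".
- **Probably Related** requires several things at once. It begins "There is evidence to suggest a causal relationship, and the influence of other factors is unlikely", and adds occurrence within a reasonable time and an event not readily attributed to a concurrent diagnosis.
- **Not Related** is met if there is no reasonable possibility of causation, or if "there is no temporal relationship between the study intervention and event onset, or an alternate etiology has been established".

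The assessor is told to use timing and clinical judgment. No time window is given, and nothing says which category prevails when two apply. Section 8.3.4 has the relationship recorded for every adverse event. Section 8.3.5 provides that "Study team members who become aware of any adverse event related to the study will notify the principal investigator" immediately, and gives a 24-hour limit for telling the IRB of a study-related death.

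**The concern.** A graded scale should become harder to satisfy as the grade rises, and each event should fit one grade. Here the top grade has the easiest entry condition, and the top and bottom grades are not mutually exclusive.

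Take a biofeedback participant who sprains an ankle at sports practice the day after a session. If the day after counts as a temporal relationship, the event is Related. Because another cause is established, it is also Not Related. One assessor could attribute a coincidental sports injury to the training. Another could clear the training of an injury to which it contributed, because a second cause had also been established. Both would be following the text.

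At stake is the label recorded for each adverse event, together with any notice whose trigger or deadline is decided by that label.

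**Working it through.** The plan states no figure on this point, so there is none to reproduce. The check is logical.

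**Inputs (section 8.3.3.2).** Five facts about an event, each true or false:
- K: known to occur with the intervention
- C: evidence suggests causality (the section's meaning of reasonable possibility)
- T: temporal relationship
- O: other factors unlikely
- A: alternate cause established

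Five facts give 2^5 = 32 patterns. O and A contradict each other, which removes 8 and leaves 24.

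**Definitions as written**
- Related = K or C or T
- Probably Related = C and O and T (the concurrent-diagnosis condition is treated as part of O; counting it separately would only make this grade stricter)
- Not Related = (not C) or (not T) or A

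**Counts**
- Related fails only when K, C and T are all absent (3 patterns): 24 − 3 = 21.
- Probably Related needs C, T and O, hence no A, with K free: 2.
- Not Related fails only when C and T hold and A does not, with K and O free (4 patterns): 24 − 4 = 20.
- Those 4 patterns all meet Related, so patterns meeting both Related and Not Related: 21 − 4 = 17.
- Probably Related but not Related: 0. Related but not Probably Related: 21 − 2 = 19.

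**Examples (K absent)**

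| Facts true | Related | Probably Related | Not Related |
|---|---|---|---|
| T only | yes | no | yes |
| T and A | yes | no | yes |
| C, T and A | yes | no | yes |
| C and T | yes | no | no |
| C, T and O | yes | yes | no |

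The last row shows the inversion: the strongest evidence pattern meets both upper grades, while timing alone in the first row also reaches the top one.

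**Sensitivity to the reading of Not Related.** If Not Related required all three of its conditions (not C, not T and A), the overlap with Related would fall from 17 patterns to 1 (K and A true, C, T and O false). The text says *or*, so this is not the natural reading. It also leaves the inversion untouched, because neither upper grade changes.

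**How often timing could be met.** Section 6.1.1 gives 12 sessions over 6 weeks, on average one every 42/12 = 3.5 days. The documents give no window, so any frequency is an assumption. Assume two sessions a week on fixed, non-consecutive days (gaps of 3 and 4 days, or of 2 and 5). A window of the session day plus the next day covers 2 × 2 = 4 of 7 days. A window running to the fourth day after a session covers all 7. The range is wide, and it applies only to the biofeedback arm in weeks 1 to 6.

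**The case against.** The strongest reply is that the defect is one of drafting and the plan has safeguards around it. Much of that stands.

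- A reader might infer that harm from the training cannot be interpreted at all. The documents do not support this. Section 8.3.4 records all adverse events whatever their relationship, so counts by randomised arm remain available. Section 8.3.6 requires a separate reasonable-possibility assessment for serious events. Section 9.4.4 plans no analysis by relatedness, and section 3 lists no safety endpoint.
- A reader might infer that nearly every event in the training period would be Related by timing. That needs a time window the plan does not give. Adverse event capture also runs beyond week 6.
- A reader might infer that the timing condition is empty because section 8.3.1 already defines an adverse event as a sign, "symptom, or disease, temporally associated with the" participant's involvement in the research. The reference points differ. An injury at the baseline assessment, before any session, meets section 8.3.1 but not the timing condition in 8.3.3.2.
- A reader might infer that any competing explanation makes an event Not Related. The text requires an alternate cause to be established.
- A reader might infer that reporting as a whole depends on the label. It does not. Under sections 8.3.5 and 8.3.6 all adverse events reach the Safety Officer twice a year and all serious events within 48 hours. A death judged unrelated is still a serious event due to the IRB within 5 business days. Section 8.4.1 has its own definition of possibly related, tied to participation in the research. The notice to the principal investigator is likewise worded around the study, not the 8.3.3.2 category, so the label matters there only where staff use it to decide.

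Clinical judgment, and the role that section 8.3.5 gives the principal investigator and Medical Monitor, may settle single cases. They do not make the result reproducible: no rule says which definition governs, and sections 8.3.3.2, 8.3.4 and 8.3.5 describe the assessor differently. The adverse event form and the manual of procedures were not available and might add guidance, but the protocol text would still contradict itself.

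**Conclusion.** The point holds as a defect in the definitions of section 8.3.3.2. Related is a weaker test than Probably Related, with no exceptions among the patterns checked, and Related and Not Related overlap in 17 of 24. The inversion does not depend on how Not Related is read; the size of the overlap does (17 patterns as written, 1 on the strict reading). These counts describe the wording and do not predict event frequencies.

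The consequence is that the relatedness label is not reproducible, and any notice decided by it (prompt notice to the principal investigator, the 24-hour notice of a study-related death) inherits that weakness. Adverse event counts by arm, reporting of serious events to the Safety Officer and the separate assessment of serious events are not affected. The text should be corrected; the efficacy results are not touched.

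The conclusion assumes that *or* has its ordinary meaning and that reasonable possibility means what the section says it means.

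**What to change.** In section 8.3.3.2, delete the clause "or there is a temporal relationship between the study intervention and event" and replace the scale with one that is ordered, exclusive and exhaustive. Assign the highest category whose conditions are all met:

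1. **Probably Related**: plausible timing, and evidence of causality, and other factors unlikely.
2. **Possibly Related** (replacing the present Related): a reasonable possibility that the intervention caused or contributed to the event, without all the conditions for category 1.
3. **Not Related**: all other events, that is, no reasonable possibility of a contribution from the intervention, for example because the timing is implausible or an established alternate cause fully accounts for the event.

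State that categories 1 and 2 both count as related for reporting. Align the terms with sections 8.3.6 and 8.4.1 and with the adverse event form.

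Check against the same 24 patterns, taking reasonable possibility as C: C holds in 12, of which 2 are Probably Related and 12 − 2 = 10 Possibly Related; the other 12 are Not Related. The total is 2 + 10 + 12 = 24, one label each. Where C holds but the assessor judges that an established other cause fully explains the event, it moves to category 3 and still has a single label.

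The cost is wording in the protocol and the form, with no added visits or data. Labels already assigned under the current text would need re-grading.
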